3.1 Primary objectives

The primary objective of this pilot study will be to determine equivalency of Zortress® as compared to Rapamune® when used in our de novo immunosuppression regimen following renal transplantation. The primary endpoint will be a composite endpoint of graft survival (non-death censored) and biopsy proven acute rejection at 1 year. The primary outcome of immunosuppressive protection would be studied in our Thymoglobulin and rapid steroid discontinuation protocol, with "half-dose" Neoral as described above.

3.2 Secondary objectives

Secondary outcomes would include factors involved with adverse events and tolerability and would include: renal graft survival (non-death censored) and biopsy proven acute rejection at 6 months, 2 and 3 years, as well as the number and grade of acute rejection episodes and responsiveness to treatment, serum creatinine and estimated GFR, results of renal biopsies at 12 months post-transplant to look for histological evidence of graft injury, early and late wound complications, infections including CMV, EBV and BK infections as monitored by serum PCR testing, lipid panel testing, particularly triglycerides, cardiac events such as acute myocardial infarctions or Congestive Heart Failure episodes, and tolerability of the Neoral and mTOR combination as determined by the patients who required conversion off of the intended randomized drug combination, with attempt to document why the patient did not tolerate the drug combination. All objectives are exploratory in nature as this is a pilot study.

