- Results of 12 month surveillance biopsies
- Lipid panels and use of lipid lowering medications at 1 year after transplant
- Incidence of MI and CHF at 1 and 3 years after transplant

- Incidence of wound infection at 1 year after transplantation
- Incidence of lymphocele at 1 year after transplantation
- Plasma concentrations of S-adenosyl homocysteine (SAH) and S-adenosyl methionine (SAM) Plasma concentrations of endothelial dysfunction markers (symmetric and asymmetric dimethyl arginine (SDMA, ADMA), L-arginine, L-citrulline, L-ornithine, cysteine, and homocysteine over the observation period
- Plasma concentrations of bioactive lipids (HODEs, HEPEs, HETEs, and prostaglandins) over the observation period
- Plasma protein patterns

Data analysis: The incidence of graft loss, patient death, and acute rejection will be compared by chi squared analyses. Patient and graft Kaplan-Meier survival curves will be compared by log rank test. We hypothesize there will be no statistically significant difference between the treatment arms. As this is a pilot study, it was not statistically powered to detect subtle differences in outcome. All continuous variables such as serum creatinine, cGFR, serum lipids, WBC, platelets, etcetera will be compared by student's t test. Any other dichotomous variables will be compared by chi squared analysis.

1 Background

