6.2 Treatment arms

Patients will be assigned to one of the following “n” treatment arms in a ratio of 2:1; Zortress or Sirolimus started on POD 0, with Solumedrol 500 mg IV in OR as induction, then 5 doses of Thymoglobulin starting morning of POD 1 at 1.25 mg/dose (rounded to nearest 25 mg) with rapid steroid taper over five doses. Neoral will be introduced as renal function recovers, usually starting on POD 2. We will enroll a total of 60 patients.

- Zortress and Neoral, with Thymoglobulin induction and perioperative steroids
- Rapamycin and Neoral, with Thymoglobulin induction and perioperative steroids

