7.1 Table 7-1

Assessment schedule:

Visit number	1 Screening/ Baseline	2	3	4	5	6	7	8	9	10	11	12	13	14	15	16	17	18
Time of Visit		Day 0	Day 1	Day 2	Day 3	Day 4	Day 5 ¹	Day 6 ¹	Day 7 ¹	Wk 2	Mo 1	Mo 2	Mo 3	Mo 6	Mo 12	Mo 18	Mo 24	Mo 36
Inclusion/Exclusion criteria	X																	
Informed consent	X																	
Physical examination	X	X	X	X	X	X	X	X	X	X	X	X	X	X	X	X	X	X
Demographics	X																	
Medical History	X																	
Pregnancy Test ²	X																	
Vital signs	X	X	X	X	X	X	X	X	X	X	X	X	X	X	X	X	X	X
Hematology		X		X				X	X	X	X	X	X	X	X	X	X	X
Chemistry		X			X			X	X	X	X	X	X	X	X	X	X	X
Lipid panel	X									X	X	X	X	X	X	X	X	X
24 hour urine												X	X	X	X	X	X	X
Alloscreen	X															X		
Flow Crossmatch	X															X		
HGB A1C																X		X
Kidney Biopsy	X															X		
Adverse events		X	X	X	X	X	X	X	X	X	X	X	X	X	X	X	X	X
Cyclosporine level ³				X				X	X	X	X	X	X	X	X	X	X	X
Everolimus level ³					X			X	X	X	X	X	X	X	X	X	X	X
Optional sub study: Plasma for Biomarkers ⁴	X				X			X	X	X	X	X	X	X	X	X	X	X

Legend:

- 1: If still inpatient
- 2: Females capable of childbearing
- 3: Cyclosporine and Zortress levels are monitored twice weekly for 0-3 months post-transplant, every two weeks for 3-12 months post-transplant, and monthly greater than 1 year post-transplant.
- 4: Plasma for biomarkers will be assessed at the University of Colorado in a subset of patients using existing plasma samples.

Patients will be followed as per the standard of care at this transplant center (The Ohio State University Medical Center, Division of Transplantation). Additional study procedures include a protocol biopsy at month 12 and some additional laboratory work at screening/baseline and at months 6, 12, 24, and 36.

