10.2 Analysis of secondary objectives

10.2.1 Efficacy (secondary)

Secondary endpoints at 6 months, 1, 2 and 3 years will include: graft survival and patient survival/death at 2 and 3 years, rate and grade of acute cellular rejection, rate of acute antibody mediated rejection, rate of new donor specific antibody formation, estimated CrCl by MDRD, lipid control as determined by requirement for anti-lipid medications and average levels with and without medications, ability to maintain initial immunosuppressive medications and reason for switch if required, wound complications as determined by need for wound packing, infection treatment with antibiotics, presence of hernia on exam and requirement for hernia repair, as well as presence of symptomatic lymphocele, and New Onset Diabetes After Transplant as determined by need for new oral or sustained Insulin medication.

Statistical analysis will be performed on SPSS or STATA software with dichotomous variables evaluated by Chi-Squared analysis, continuous variables by Student's T-Test, non-parametric outcomes will be assessed by Wilcoxon rank sum test (Mann-Whitney U test). Kaplan-Meier survival curves with log rank tests will be used to determine a difference in graft and patient survival over time.

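### Under the plan's generic unadjusted tests, the month-12 histology comparison would ignore the scheduled baseline kidney biopsy and donor type, so lesions already present at implantation would count as graft injury in both arms

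*Combined protocol and SAP*

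**What the plan says.** - **Outcome.** Section 3.2 gives the histology outcome as "results of renal biopsies at 12 months post-transplant to look for histological evidence of graft injury". The synopsis, under other assessments, has "Results of 12 month surveillance biopsies". No lesion definition, score or baseline reference is given.
- **Schedule.** In Table 7-1 the row "Kidney Biopsy" is marked at screening/baseline and once later. The text below the table reads "Additional study procedures include a protocol biopsy at month 12 and some additional laboratory work at screening/baseline". It does not describe the baseline biopsy, say which kidney it samples, or say whether every patient has one.
- **Analysis.** The secondary endpoint lists in sections 10.1.2 and 10.2.1 cover "rate and grade of acute cellular rejection, rate of acute antibody mediated rejection, rate of new donor specific antibody formation" and other items, but not the month-12 biopsy. The remaining rules are generic. The synopsis has "Any other dichotomous variables will be compared by chi squared analysis", and section 10.2.1 has "continuous variables by Student's T-Test, non-parametric outcomes will be assessed by Wilcoxon rank sum test (Mann-Whitney U test". None includes a covariate or a stratification factor.
- **Design.** "We will enroll a total of 60 patients" (section 6.2), allocated 2:1, which gives about 40 on Zortress and 20 on Rapamune. Section 6.3 stratifies randomisation by living or deceased donor and by primary or repeat transplant.

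**The concern.** The stated aim is to find injury to the graft. A biopsy read at month 12 alone shows two things together: lesions that came with the donor kidney, and lesions that arose or progressed after transplant. Only the second kind can reflect the regimen. The trial takes both living- and deceased-donor kidneys, so the amount of pre-existing damage may well vary between patients.

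If the generic tests are applied as they stand, an unchanged inherited lesion scores the same as a new one. The baseline biopsy and the donor-type stratum could help to separate the two, yet the plan uses neither. At stake are the absolute injury rates reported for each regimen, the size of any difference between arms, and the precision of a comparison that has at most about 20 patients in its smaller arm. Graft loss and missed biopsies would lower that number further.

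**Working it through.** The documents give no lesion rate, score SD, correlation or power for histology, so there is no planned figure to reproduce. What follows is illustration. The arm sizes (40 and 20) come from the documents. The prevalences, new-lesion risks, correlations and two-sided 5% level are assumptions, and every patient is taken to have a biopsy.

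**1. Inflated rates and dilution (binary lesion).** Let d be the share of kidneys with the lesion at implantation, assumed to persist, and p the risk of a new lesion. The month-12 rate is q = d + (1 - d)p. The arm difference is therefore (1 - d) times the true difference.

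Assume p = 20% v 40%, a true gap of 20 points. At d = 30%:
- q = 0.30 + 0.70 × 0.20 = 0.44
- q = 0.30 + 0.70 × 0.40 = 0.58
- gap = 0.14, and a 20% new-injury rate reads as 44%

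Power = Φ((gap - 1.96 × SE0)/SE1), where SE0 is the pooled and SE1 the unpooled standard error:

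| d | Month-12 gap | Power, month 12 alone | Power, kidneys lesion-free at baseline |
|---|---|---|---|
| 10% | 18 points | 29% | 35% |
| 30% | 14 points | 17% | 29% |
| 50% | 10 points | 11% | 22% |

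If new or worsened lesions could be counted at the same risks in all 60 patients, power would be 38%. That is an upper figure, because worsening may be harder to detect in a kidney that already has the lesion.

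**2. Chance imbalance.** Ignoring stratification, the SD of the arm difference in inherited lesions is sqrt(d(1 - d)(1/40 + 1/20)). For d = 10%, 20%, 30% and 40% this is 0.082, 0.110, 0.125 and 0.134. The exact binomial probability of a gap of at least 10 points is 28%, 42%, 49% and 52%. For at least 20 points it is 2%, 9%, 14% and 16%.

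Stratifying by donor type helps a little. With equal strata and assumed rates of 5% (living) and 35% (deceased), 20% overall, the mean within-stratum variance is (0.05 × 0.95 + 0.35 × 0.65)/2 = 0.1375. The SD is sqrt(0.1375 × 0.075) = 0.102, against 0.110 without stratification.

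**3. Check for bias.** With equal new-lesion risk in both arms (d = 30%, p = 20%), 200,000 simulated trials gave a mean arm difference of 0.000 and a type I error of about 5.3% for the unadjusted test.

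**4. Precision (graded score treated as continuous).** With correlation ρ between baseline and month 12, adjustment removes ρ² of the variance. For ρ = 0.3 to 0.6 that is 9% to 36%, equivalent to 1/(1 - ρ²) = 1.10 to 1.56 times the patients.

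The difference detectable with 80% power from month 12 alone is (1.96 + 0.84) × sqrt(1/20 + 1/40) = 0.77 SD. Covariate adjustment multiplies this by sqrt(1 - ρ²), and a change score by sqrt(2(1 - ρ)):

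| ρ | Month 12 alone | Adjusted for baseline | Change score |
|---|---|---|---|
| 0.3 | 0.77 | 0.73 | 0.91 |
| 0.5 | 0.77 | 0.66 | 0.77 |
| 0.7 | 0.77 | 0.55 | 0.59 |

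A plain change score is worse than month 12 alone when ρ is below 0.5. Adjustment is never worse in this approximation.

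**The case against.** The strongest reply is that randomisation deals with this. Inherited lesions precede treatment, occur in both arms, and balance in expectation, and stratification by donor type helps further. A 10-point gap at 40 v 20 is about one standard error, which is ordinary sampling error already covered by the test. This stands. A reader might infer that inherited lesions are charged to the study drug and so tilt the comparison against Zortress. The documents do not support that, and the simulation shows no such tilt. What randomisation does not do is remove the dilution, correct the inflated absolute rates, or recover the lost precision.

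A second reply is that the plan never states an unadjusted month-12 comparison. Also correct: no histology analysis is written, and the naming of the outcome does not rule out reading against baseline. The unadjusted comparison is what follows if the generic rules are applied.

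Third, the baseline biopsy may not be a sample of the donor kidney, may not exist for every patient, and may not be scored in the same way. The documents do not settle this, so a claim that the fix needs no extra reading work would go too far.

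Fourth, section 3.2 calls all objectives exploratory, and sections 10.3 and 10.4 say that the trial is not powered. That limits the importance of the point but is no reason to leave a scheduled measurement unused.

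**Conclusion.** The point holds as a low-cost improvement of modest importance. Applied as written, the generic tests would mix inherited with new injury in both arms. The consequences are inflated absolute rates, a true difference shrunk by (1 - prevalence), and some chance imbalance and lost precision. There is no systematic bias and no meaningful loss of type I error control.

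On the assumed values, a 20-point gap in new lesions reads as 18 points at 10% prevalence, 14 at 30% and 10 at 50%. Baseline adjustment removes 9% to 36% of the variance at correlations of 0.3 to 0.6. The dilution figures assume that inherited lesions persist to month 12; the precision figures treat the score as roughly continuous. The imbalance probabilities ignore stratification and are therefore somewhat high. The direction of the dilution deserves note, since the synopsis expects the arms not to differ on its main outcomes: a diluted histology result would lean the same way.

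**What to change.** - Analyse graded month-12 scores adjusted for the baseline score and donor type, by ordinal regression or rank ANCOVA, not as a plain change score.
- Report binary lesions as new or worsened relative to the same kidney's baseline biopsy.
- Give the unadjusted month-12 results alongside.
- State that the baseline biopsy is of the transplanted kidney. Where no such sample exists, adjust for donor type alone; no biopsy should be added for this purpose.
- Check the later mark in the Table 7-1 biopsy row against the month-12 text. In the text as extracted it falls under month 18, which may only be a column shift, so reconcile the two if the original table shows the same.

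The cost is a few sentences of analysis plan and slightly more analysis. If baseline specimens exist but are not routinely scored on the same scale, there is also the work of scoring them, which the documents do not describe.

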Two prospective randomized trials (A2306 and A2307) have demonstrated that everolimus combined with steroids and low dose Neoral with (A2307) or without (A2306) basiliximab induction result in excellent 1 year outcomes (1). In 2002 we adopted an immunosuppressive regimen using Rapamune and reduced dose Neoral without steroids using induction therapy with Thymoglobulin. Since employing this regimen our acute rejection rate within the first year post-transplant has been between 7% and 10% for any given calendar year. However, many patients need to have their Rapamune discontinued due to drug related side effects or compliance difficulties related to the noon dosing (when most other medications are taken at 8 am and 4 pm). We feel strongly that use of an alternative drug to Rapamune in such cases is necessary. Use of Zortress in this setting would be ideal, however, no data currently exists concerning the use of Zortress with Neoral in a steroid free maintenance immunosuppression regimen following Thymoglobulin induction. Thus we propose this pilot study primarily to verify Zortress efficacy using our established immunosuppressive protocol. Secondarily we are interested in characterizing the Zortress drug related side effect profile to enable us in the future to exploit any favorable differences between Zortress and Rapamune.

2 Purpose and rationale

Our center's renal transplant immunosuppression protocol has consisted of Thymoglobulin and steroid induction for 5 doses only, with early initiation of Rapamune® (Sirolimus) and then Neoral for nearly a decade now. We do observe a significant amount of adverse events in our patient population, with many of these potentially related to the Sirolimus. The combination of "half-dose" cyclosporine (early C2 levels around 800 to 1000 ng/ml) allows us to minimize calcineurin inhibitor toxicity and its combination with the mTOR drug Sirolimus provides excellent protection against acute rejection in our renal transplant recipients. Our earlier experience with Everolimus and the recent publications describing renal recipients' outcomes with this drug, suggest to us that our patients may do better on Everolimus than Sirolimus (1,2). For our center, this pilot study would be very straightforward as the only difference in medication from our current well established protocol would be the randomization to either Rapamune®, our current standard of care, or Zortress®, the study drug.

3 Objectives

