7.5 Efficacy

7.5.1 Efficacy assessment 1

- Incidence of graft loss in the first post-transplant year
- Incidence of patient death in the first post-transplant year
- Incidence of biopsy proven acute rejection at 1 year post-transplant
- Tolerability of Zortress at 1 year post-transplant
- Renal function at 1 year post-transplant

8 Safety monitoring

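### The only worded tolerability outcome counts leaving Neoral or the mTOR drug, so a difference between arms cannot be attributed to the mTOR drug, and fixed-time chi-squared tests have no place for death, graft loss or censoring before conversion.

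*Combined protocol and SAP*

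**What the plan says.** Section 3.2, repeated in the synopsis, gives the only worded definition: "tolerability of the Neoral and mTOR combination as determined by the patients who required conversion off of the intended randomized drug combination". On the reasons for conversion, the same section commits only to proceed "with attempt to document why the patient did not tolerate the drug combination". Sections 10.1.2 and 10.2.1 restate the idea as "ability to maintain initial immunosuppressive medications and reason for switch if required", among endpoints listed for 6 months and 1, 2 and 3 years. Section 7.5.1 and the synopsis list "Tolerability of Zortress at 1 year post-transplant", with no definition and no Rapamune counterpart.

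Section 6.2 gives the arms as "Zortress and Neoral, with Thymoglobulin induction and perioperative steroids" and "Rapamycin and Neoral, with Thymoglobulin induction and perioperative steroids". Section 2 says that "the only difference in medication from our current well established protocol would be the randomization to either Rapamune" or Zortress. Section 1 reports that "many patients need to have their Rapamune discontinued due to drug related side effects or compliance difficulties" arise under the current regimen.

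Sections 10.1.2 and 10.2.1 send dichotomous variables to chi-squared and name Kaplan-Meier with log-rank only for graft and patient survival. Section 10.1.3 censors patients lost to follow-up or discontinued from the study. Section 6.5.4 records adjustments and interruptions of drug. Section 6.5.5 allows the mTOR drug to be stopped for side effects, infection or malignancy.

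**The concern.** Section 1 names the side-effect profile of Zortress against Rapamune as the secondary interest, and the background problem is patients coming off Rapamune. One would expect an outcome that counts coming off the randomised mTOR drug, defined identically in both arms. The plan has none. The worded outcome mixes the randomised drug with a background drug, and the drug-specific item covers one arm.

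Two things are at stake. First, an observed difference, or its absence, could come from Neoral stopping, and no planned analysis would separate the two. Secondly, a proportion at a fixed time needs every patient classified as converted or maintained. The plan does not say which applies to a patient who dies or loses the graft on the assigned drugs, and a chi-squared test on a proportion cannot use censored follow-up.

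**Working it through.** The plan states no conversion rate, significance level or power, so there is no figure of its own to reproduce. What follows is illustration.

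**From the documents:** 60 patients allocated 2:1 (section 5), hence 60 × 2/3 = 40 Zortress and 60 × 1/3 = 20 Rapamune; chi-squared for dichotomous variables (section 10.2.1).

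**Assumed:** two-sided 5% level; one-year mTOR stopping p of 10% (Zortress) v 35% (Rapamune), with 15% v 45% and 20% v 40% as alternatives; Neoral stopping q, independent of mTOR stopping within each arm.

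**Formulas.** Risk of leaving the combination = 1 − (1 − p)(1 − q). If q is the same in both arms, the risk difference is (1 − q)(p_Rapamune − p_Zortress), so it shrinks by the factor (1 − q). Power is the exact probability, over all pairs of binomial(40) and binomial(20) counts, that the uncorrected chi-squared statistic exceeds 3.841.

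**Equal Neoral stopping, 10% v 35%:**

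| q in both arms | Zortress | Rapamune | Difference (points) | Power |
|---|---|---|---|---|
| 0% | 10.0% | 35.0% | 25.0 | 63.5% |
| 5% | 14.5% | 38.25% | 23.75 | 54% |
| 10% | 19.0% | 41.5% | 22.5 | 46% |
| 20% | 28.0% | 48.0% | 20.0 | 34% |

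For example, at q = 20%: Zortress 1 − 0.90 × 0.80 = 28%; Rapamune 1 − 0.65 × 0.80 = 48%; difference 0.80 × 25 = 20 points.

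With 15% v 45%, power is 71%, 63%, 56% and 44% at the same four values of q. With 20% v 40%, it is 38% at q = 0 and 23% at q = 20%.

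**Unequal Neoral stopping, 10% v 35%:**
- 5% Zortress, 15% Rapamune: 1 − 0.90 × 0.95 = 14.5% v 1 − 0.65 × 0.85 = 44.75%. The difference is 30.25 points, more than the mTOR-only 25, and power is 72%.
- 15% Zortress, 5% Rapamune: 1 − 0.90 × 0.85 = 23.5% v 1 − 0.65 × 0.95 = 38.25%. The difference is 14.75 points and power is 23%.

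So the regimen-level difference can lie on either side of the mTOR-only difference.

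**Analysis method.** Setting sections 10.1.2, 10.1.3 and 10.2.1 side by side: time-to-event methods are named for graft and patient survival only, so maintenance of medication falls to chi-squared at each time point. Censoring is the only rule for incomplete follow-up, and it has no meaning in that test. No section classifies death or graft loss for this outcome. The size of the resulting error was not calculated, because the documents give nothing on how these events would relate to conversion.

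**The case against.** Tolerability of the whole regimen is a legitimate question, and section 3.2 names the combination as its target. If the mTOR drug affects whether a patient can stay on Neoral, conversion off Neoral is part of the treatment effect. This stands, and it is why the regimen-level outcome should be kept.

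The information is also not lost. Reasons for conversion are sought in sections 3.2 and 10.2.1, and mTOR changes are recorded under section 6.5.4, so a drug-specific split could be derived later. That stands only in part. The trial is open-label and dose changes are at the physician's discretion, so a definition chosen after the data are seen is weaker than one fixed beforehand.

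An outcome that counts mTOR stops for any reason has noise of its own, since section 6.5.5 allows stops for infection or malignancy. This also stands, and it argues for counting intolerance separately.

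A reader might infer three stronger points, none of which the documents support:
- **Neoral stops necessarily dilute the contrast.** That needs similar Neoral stopping in both arms, and no rate is given for either arm.
- **The trial exists because patients stop Rapamune, so this outcome is its best chance of a difference.** Section 1 puts verifying efficacy first and side effects second, and nothing supports the ranking.
- **An arm with more early deaths or graft losses will look better tolerated.** This is possible, but it depends on a classification that the plan does not state.

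**Conclusion.** The point holds as one of attribution and method. No tolerability outcome isolates the mTOR drug in both arms, the sections that mention tolerability do not agree, and the fixed-time tests do not accommodate death, graft loss or censoring before conversion.

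The numerical effect is conditional. Under the assumed 10% v 35%, equal Neoral stopping of up to 20% takes power from 63.5% to 34%; unequal stopping of 5% and 15% takes it to 72% or 23%, depending on the arm. These rest on assumed rates, independence of the two kinds of stop, and a two-sided 5% level.

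Materiality is limited. Section 3.2 calls all objectives exploratory, and sections 10.3 and 10.4 say the trial is not powered. At an assumed 20% v 40%, even the mTOR-only outcome has 38% power. The case for change is a clearer and cheaply obtained comparison, without any claim that the trial would become adequately powered.

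**What to change.** Keep conversion off the combination as a regimen-level outcome. Add, for both arms, permanent discontinuation of the assigned mTOR drug, counted (a) for intolerance and (b) for any reason, including the infection and malignancy stops in section 6.5.5. Report Neoral-only stops separately by arm.

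Analyse time from transplantation to discontinuation by cumulative incidence, with death and graft loss as competing events. For (a), treat stops for other reasons as competing too. Use one between-arm test over follow-up, such as Gray's test, in place of tests at four time points. The cumulative incidences at 6 months and 1, 2 and 3 years can still be shown as estimates.

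Align the synopsis (objectives and assessment list) and sections 3.2, 7.5.1, 10.1.2 and 10.2.1, and extend the Zortress-only item to Rapamune.

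The cost is mainly wording, with one data requirement. Stop date and reason must be captured consistently for both the mTOR drug and Neoral. Section 6.5.4 speaks of Zortress and Sirolimus changes and does not mention dates or reasons; section 3.2 promises only an attempt at the reason. No change in patient care is involved.
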